#### 7.7. Toxicity Management

#### 7.7.1. **GS-5245**

All clinical and clinically significant laboratory toxicities will be managed according to the guidelines described below.

The Gilead medical monitor should be consulted prior to study drug discontinuation when medically feasible. Before discontinuation of study drug for AEs or laboratory abnormalities, an assessment of the participant's medical situation should be made by the investigator.

For Grade 3 and Grade 4 clinically significant laboratory abnormalities that need to be confirmed by repeat testing, a local laboratory may be used if urgent results are needed for participant safety. However, a concurrent second set of blood samples should be drawn and sent to the central laboratory for proper documentation and data integrity.

7.7.1.1. Laboratory Events Meeting Discontinuation Criteria

Laboratory events meeting discontinuation criteria are discussed in Section 3.3.1.1.

7.7.1.2. Grades 1 and 2 Laboratory Abnormality or Clinical Event

Continue study drug at the discretion of the investigator.

7.7.1.3. Grade 3 Laboratory Abnormality or Clinical Event

For a Grade 3 clinically significant laboratory abnormality or clinical event, study drug may be continued if the event is considered to be unrelated to study drug.

For a Grade 3 clinically significant laboratory abnormality or clinical event confirmed by repeat testing, that is considered to be related to study drug, **the participant will be discontinued from study drug**. The participant should be managed according to local practice.

Additionally, participants who have a  $CL_{cr} < 50 \text{ mL/min}$  (by Cockcroft-Gault equation) will be discontinued from study drug whether considered related to the study drug or not (refer to Section 3.3.1.1).

Recurrence of laboratory abnormalities considered unrelated to study drug may not require permanent discontinuation but requires discussion with the Gilead medical monitor.

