#### **3.3. Protocol-Specific Discontinuation Criteria**

#### **3.3.1.** Criteria for Early Discontinuation for the Individual Participants

3.3.1.1. Criteria for Early Discontinuation for the Individual Participants From Study Intervention

Study drug will be discontinued in the following instances:

- An SAE suspected to be related to study drug.
- Any  $\geq$  Grade 3 clinically significant AE suspected to be related to study drug.
- An AE, or worsening of clinical condition requiring clinical intervention, that would, in the judgment of the investigator, affect assessments of clinical status to a significant degree.
- Any ≥ Grade 3 clinically significant laboratory abnormality (if confirmed by repeat testing) suspected to be related to study drug.
   Except if baseline or on-treatment CLcr < 50 mL/min or eGFR < 50 mL/min/1.73m^2, then study drug is to be discontinued without confirmation by repeat testing and irrespective of relatedness.
- Unacceptable toxicity, as defined in Section 7.7, or toxicity that, in the judgment of the investigator, compromises the ability to continue study-specific procedures or is considered not to be in the participant's best interest.
- Baseline or on-treatment alanine aminotransferase (ALT)  $\geq$  5 × ULN.

- Baseline or on-treatment bilirubin  $\ge 2 \times ULN$  ( $\ge 3 \times ULN$  for participants with Gilbert's syndrome).
- Participant request to discontinue for any reason.
- Participant noncompliance.
- Pregnancy (refer to Appendix 11.3).
- Discontinuation of the study by sponsor.

If a participant discontinues study drug, every attempt should be made to keep the participant in the study and continue to perform the required study-related follow-up and procedures.

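### Protocol 3.3.1.1 stops study drug for ALT or bilirubin over a limit without conditions, 7.7.1.3 lets an unrelated Grade 3 laboratory abnormality continue, and neither section says which governs

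*Protocol*

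**What the plan says.** Protocol 3.3.1.1 opens its list with "Study drug will be discontinued in the following instances". Four entries matter here.

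- ALT at or above 5 × ULN, at baseline or on treatment. No further condition is attached.
- "Baseline or on-treatment bilirubin" at or above 2 × ULN (3 × ULN in Gilbert's syndrome). Again no further condition.
- The general Grade 3 or higher laboratory entry, which does carry conditions: "clinically significant laboratory abnormality (if confirmed by repeat testing) suspected to be related to study drug". Its renal exception, for CLcr or eGFR below 50, adds that "then study drug is to be discontinued without confirmation by repeat testing and irrespective of relatedness".
- A related, clinically significant adverse event of Grade 3 or higher. Repeat testing is not mentioned.

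Protocol 7.7.1 then says that clinical and clinically significant laboratory toxicities are to be managed by the rules that follow it. Section 7.7.1.1 is a one-line pointer saying that laboratory events meeting stopping criteria are discussed in 3.3.1.1. For Grades 1 and 2, 7.7.1.2 says "Continue study drug at the discretion of the investigator". For Grade 3, 7.7.1.3 says "study drug may be continued if the event is considered to be unrelated to study drug". It names one exception, CLcr below 50, which applies "whether considered related to the study drug or not (refer to Section 3.3.1.1". For Grade 4, 7.7.1.4 stops drug for confirmed, related, clinically significant events. It permits continuation for a laboratory abnormality that is not clinically significant, or for an unrelated clinical event.

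**The concern.** Two sections give stopping instructions for the same laboratory results on different terms. For ALT and bilirubin, 3.3.1.1 depends only on the value. Section 7.7.1.3 depends on the investigator's view of relatedness. Because 7.7.1.3 singles out creatinine clearance as applying whatever the cause, a reader who starts there could infer that ALT and bilirubin follow the relatedness rule.

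Two things are at stake. The first is safety. Screening liver tests are optional outside South Africa and the United Kingdom (Table 1 footnote i, Appendix 11.4), and samples after screening go to the central laboratory (6.3.2.5). A baseline value over the limit may therefore become known only after dosing has begun.

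The second is the secondary endpoint of adverse events leading to study drug discontinuation. Under protocol 7.6, a laboratory abnormality that leads to discontinuation must be recorded as an adverse event. Under SAP 7.1.5.1, any adverse event leading to premature discontinuation is treatment-emergent. The section a site follows can thus decide whether an event enters that count at all.

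**Working it through.** No arithmetic applies, and the plan gives no figure to reproduce. The check sets each stopping criterion in 3.3.1.1 beside the rule in 7.7 that would also apply to it.

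| Situation | 3.3.1.1 | 7.7.1.2 to 7.7.1.4 | Result |
|---|---|---|---|
| ALT or bilirubin over the limit, Grade 3, clinically significant, judged unrelated | Stop | Continuation permitted (7.7.1.3) | Mismatch |
| ALT or bilirubin over the limit, Grade 4, not clinically significant | Stop | Continuation permitted (7.7.1.4) | Mismatch |
| ALT or bilirubin over the limit, Grade 4, clinically significant, not confirmed on repeat | Stop | Managed by the rule for the new grade (7.7.1.4) | Different route; outcome depends on the new grade |
| ALT or bilirubin over the limit, Grade 4, clinically significant, judged unrelated | Stop | No express permission to continue (7.7.1.4) | No express mismatch |
| ALT or bilirubin over the limit, Grade 1 or 2 | Stop | Investigator discretion (7.7.1.2) | Cannot be shown: grading table not reproduced |
| CLcr below 50 | Stop, whatever the cause | Stop, whatever the cause (7.7.1.3) | Agrees |
| eGFR below 50 | Stop, whatever the cause | Not named; 7.7.1.3 refers to 3.3.1.1 | Largely covered by the reference |
| Related, clinically significant clinical event, Grade 3 or higher | Stop; no repeat testing | Worded with confirmation by repeat testing (7.7.1.3, 7.7.1.4) | Smaller mismatch |

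The next question is whether 7.7.1.1 removes the mismatches.

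1. It sends laboratory events meeting stopping criteria to 3.3.1.1, so the sections are linked.
2. It says where those events are discussed. It does not say that the graded rules give way to 3.3.1.1.
3. The references run both ways: 3.3.1.1 relies on 7.7 for its definition of unacceptable toxicity.
4. Despite the pointer, 7.7.1.3 restates one exception and leaves out ALT and bilirubin.
5. The pointer concerns laboratory events only, so it cannot settle the wording on clinical events.

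On timing, dosing lasts 5 days. Safety laboratories are drawn on Days 1 and 5, on Days 3 and 15 if the visit is in person, and at early discontinuation. A Day 15 result cannot change dosing, and a Day 5 result will usually come at or near the end of the course. The scheduled results most likely to matter are therefore Day 1 and an in-person Day 3.

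**The case against.** The strongest reply is that the text resolves itself. Section 7.7.1.1 stands ahead of the graded rules and refers these events to 3.3.1.1. That section is mandatory and specific, while 7.7.1.3 is general and permissive, so ordinary reading gives 3.3.1.1 precedence. Sites also have an arbiter: the medical monitor is to be consulted before discontinuation when feasible, and takes questions on toxicity management. Much of this stands. It makes the problem an incomplete carry-over between linked sections. But precedence has to be inferred, and a site that sees no ambiguity has no reason to ask.

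Several stronger readings are tempting and are not supported.

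- A reader might infer a flat contradiction with no bridge. Section 7.7.1.1 is a bridge, though an incomplete one.
- A reader might take 3.3.1.1 to state outright that ALT and bilirubin stop drug whatever the cause. Those words attach only to CLcr and eGFR; for the liver tests the meaning is inferred from the absence of conditions.
- A reader might take 7.7.1.4 to let a Grade 4 laboratory value continue if unrelated. There, unrelatedness qualifies clinical events only.
- A reader might see a conflict with 7.7.1.2. That needs a value over the limits to be Grade 1 or 2, which the documents cannot show.
- A reader might treat the missing eGFR limit in 7.7.1.3 as a separate renal rule. The reference to 3.3.1.1 largely covers it, and 6.3.2.5 itself describes eGFR by the Cockcroft-Gault equation.

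On repeat testing of clinical events, the phrase may have been meant for laboratory results only. As written, it covers both.

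**Conclusion.** The point holds as an internal inconsistency of limited reach. Section 7.7.1.3 as written would allow dosing to continue for a Grade 3 ALT or bilirubin abnormality judged unrelated, where 3.3.1.1 requires a stop, and the pointer between them does not state precedence. The confirmation wording for related clinical events is a second, smaller mismatch.

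This rests on one assumption: that some values over the 3.3.1.1 limits are Grade 3. The limits have no upper bound, but the grading table is not in the documents.

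The size cannot be calculated, because no expected frequency is given. The primary and key secondary efficacy analyses should be little affected, since protocol Table 11 and SAP Table 6-1 handle treatment discontinuation by treatment policy. The relevance is to participant safety and to the count of adverse events leading to study drug discontinuation. Nothing in the documents shows that the effect on that count would favor either arm.

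**What to change.** Reconcile protocol 3.3.1.1 with 7.7.1.1 to 7.7.1.4 so that the same criteria, renal measures and confirmation wording appear in both places, and state which section governs when both apply. Which clinical rule applies is for the sponsor's medical team; no view is taken here.

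The cost is protocol wording and a site clarification, with no effect on sample size or planned analyses. SAP 2.3 records that enrollment stopped on 06 October 2023, so a clarification now has little practical use for dosing.

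What can still be done is in the clinical study report: list participants whose baseline or on-treatment ALT or bilirubin met the 3.3.1.1 limits, with whether and when study drug was stopped. The liver summary in SAP 7.2.3 does not identify quite this group, because it covers postbaseline values only and uses strict inequalities (above 5 × ULN and above 2 × ULN). The listing needs only data already collected.

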7.7.1.4. Grade 4 Laboratory Abnormality or Clinical Event

For a Grade 4 clinically significant laboratory abnormality or clinical event confirmed by repeat testing, that is considered to be related to study drug, **the participant will be discontinued from study drug**. The participant should be managed according to local practice. The participant should be followed as clinically indicated until the laboratory abnormality returns to baseline or is otherwise explained, whichever occurs first. A clinically significant Grade 4 laboratory abnormality that is not confirmed by repeat testing should be managed according to the algorithm for the new toxicity grade.

Study drug may be continued without dose interruption for a clinically nonsignificant Grade 4 laboratory abnormality (eg, Grade 4 creatine kinase elevation after strenuous exercise or triglyceride elevation that is nonfasting or that can be medically managed) or a clinical event considered unrelated to study drug.

Treatment-emergent toxicities will be noted by the investigator and brought to the attention of the Gilead medical monitor, and the appropriate course of action will be discussed and decided. Whether or not considered treatment-related, all participants experiencing AEs must be monitored periodically until symptoms subside, any abnormal laboratory values have resolved or returned to baseline levels or they are considered irreversible, or until there is a satisfactory explanation for the changes observed.

Any questions regarding toxicity management should be directed to the Gilead medical monitor.

# 8. STATISTICAL CONSIDERATIONS

Details of the statistical methods will be provided in the statistical analysis plan, including any deviations from the original statistical analyses planned.

#### 8.1. Analysis Objectives and Endpoints

Objectives and endpoints are listed in Section 2.

#### 8.2. Planned Analyses

#### 8.2.1. Interim Analysis

Before the final analysis, interim analyses will be conducted, and the analyses may be submitted to regulatory agencies to seek guidance for the overall clinical development program.

#### 8.2.1.1. Data Monitoring Committee Analysis

The first DMC meeting will be based on data collected after the first 200 participants have reached Day 29 or prematurely discontinued from the study and will include safety data.

The second DMC meeting will be based on data collected after 50% of planned participants complete the Day 29 assessment or prematurely discontinue from the study, or 50% of expected primary endpoint events occur, whichever happens earlier. The DMC meeting will include review of safety and formal evaluation of futility and efficacy. The DMC may provide recommendation on stopping enrollment to the study if the prespecified boundaries for efficacy (outlined in Section 8.7) or futility are crossed. If the second DMC meeting is triggered by 50% planned enrollment, a third DMC meeting may be conducted after 50% of expected primary endpoint events as appropriate. If the second DMC meeting is triggered by 50% of expected primary endpoint events, a third DMC meeting is not planned. An interim analysis communication plan will be created.

Further details are provided in the DMC charter.

#### 8.2.2. Final Analysis

The unblinded final analysis will be performed after all participants have completed the study, outstanding data queries have been resolved or adjudicated as unresolvable, and the data have been cleaned and finalized. Unless efficacy or futility boundaries are crossed at the interim analysis, the analysis of the primary endpoint of COVID-19–related hospitalization or all-cause death by Day 29 and key  $\alpha$ -controlled secondary endpoints will be conducted at the time of the final analysis. The overall type I error rate will be controlled at the two-sided 0.05 significance level using the Lan-DeMets approach with O'Brien-Fleming type spending function.

#### 8.3. Analysis Conventions

#### 8.3.1. Analysis Sets

#### 8.3.1.1. Efficacy

The primary analysis set for efficacy analyses is defined as the Full Analysis Set (FAS), which will include all participants who (1) are randomized into the study and (2) have received at least 1 dose of study drug. Participants will be grouped according to the treatment to which they were randomized.

8.3.1.2. Safety

The primary analysis set for safety analyses is defined as the Safety Analysis Set, which will include all participants who (1) are randomized into the study and (2) have received at least 1 dose of study drug. Participants will be grouped according to the treatment which they received.

All data collected during treatment plus 30 days will be included in the safety summaries.

#### 8.3.1.3. Virology

The Virology Analysis Set will include all participants who (1) are randomized into the study, (2) have received at least 1 dose of study drug, and (3) have positive SARS-CoV-2 viral load at baseline. Participants will be grouped according to the treatment they received.

#### 8.3.1.4. Pharmacokinetics

The PK Analysis Set will include all randomized participants who received at least 1 dose of GS-5245 and had at least 1 nonmissing PK concentration datum reported by the PK laboratory for each respective analyte.

CCI	

#### 8.3.2. Data Handling Conventions

Natural logarithm transformation for PK parameters will be applied for PK analysis.

For summary statistics, PK concentration values below the limit of quantitation will be treated as zero at predose and one-half of the lower limit of quantitation (LLOQ) for postdose time points.

Laboratory data that are continuous in nature but are less than the LLOQ or above the upper limit of quantitation, will be imputed to the value of the lower or upper limit plus or minus 1 significant digit, respectively (eg, if the result of a continuous laboratory test is < 20, a value of 19 will be assigned).

Missing data can have an impact upon the interpretation of the study data. In general, values for missing data will not be imputed. However, a missing pretreatment laboratory result would be treated as normal (ie, no toxicity grade) for the laboratory abnormality summary.

All available data for participants that do not complete the study will be included in data listings.

#### 8.4. Demographic and Baseline Characteristics Analysis

Demographic and baseline measurements will be summarized using standard descriptive methods.

Demographic summaries will include sex, race/ethnicity, randomization stratification group, age. For categorical demographic and baseline characteristics, a Cochran-Mantel-Haenszel test will be used to compare treatment groups. For continuous demographic and baseline characteristics, a Wilcoxon rank sum test will be used to compare treatment groups.

#### 8.5. Efficacy Analysis

#### 8.5.1. Primary Analysis

The primary endpoint is the proportion of COVID-19–related hospitalization or all-cause death by Day 29. COVID-19–related hospitalization is defined as  $\geq$  24 hours of acute care for a reason related to COVID-19, in a hospital or similar acute care facility, including emergency rooms or temporary facilities instituted to address medical needs of those with COVID-19. This includes specialized acute medical care units within an assisted living facility or nursing home. This does not include hospitalization for the purposes of public health and/or clinical study execution. The date and duration of hospital admission, and primary reason for hospitalization (including if the hospitalization is related to COVID-19) will be recorded.

The primary endpoint will be analyzed using a Cox proportional hazards model with the stratification factors (duration of symptoms and vaccination status) as covariates. The hazard ratio and 95% CI will be provided. Handling of intercurrent events is defined in Section 8.5.3.

The number and percentage of participants with COVID-19–related hospitalization or all-cause death by Day 29, and reasons for missing data will be summarized.

The FAS will be used for the primary efficacy endpoint analysis.

Sensitivity analyses may be conducted using the following alternative approaches for the primary endpoint.

- Missing hospitalization status will be imputed using multiple imputation assuming missing at random.
- A participant with missing hospitalization status will be imputed as the participant was hospitalized.

# 8.5.2. Secondary Analyses

The secondary endpoints of COVID-19–related MAVs or all-cause death by Day 29 and all-cause death will be analyzed similarly as in the primary analysis. The secondary endpoints of all-cause hospitalization by Day 29 and COVID-19–related MAVs will be analyzed using a competing risk analysis approach, with death as the competing risk.

Medically attended visits are defined as any interactions with health care professionals other than study staff or designees including hospitalization; in-person emergency, urgent, or primary care visits; or any other in-person visit attended by the participant and a health care professional. The nature and cause of the visit should be identified.

All-cause hospitalization is defined as  $\geq 24$  hours of acute care, in a hospital or similar acute care facility, including emergency rooms or temporary facilities instituted to address medical needs of those with COVID-19. This includes specialized acute medical care units within an assisted living facility or nursing home. This does not include hospitalization for the purposes of public health and/or clinical study execution. The date and duration of hospital admission, and primary reason for hospitalization (including if the hospitalization is related to COVID-19) will be recorded.

A gatekeeping approach will be used for testing the key secondary endpoints. The endpoints will be tested in the following sequential order:

- Proportion of participants with all-cause hospitalization by Day 29.
- Proportion of participants with COVID-19-related MAVs or all-cause death by Day 29.
- Proportion of participants with COVID-19-related MAVs by Day 29.

Change from baseline in SARS-CoV-2 nasal swab viral load to Day 5 will be summarized by treatment groups and compared between treatment groups using a mixed-effects model repeated measures (MMRM) approach.

The Kaplan-Meier product limit method will be used to estimate, and log-rank test will be used to compare treatment groups for the time to symptom alleviation of targeted COVID-19 symptoms.

Handling of intercurrent events for key secondary efficacy endpoints is defined in Section 8.5.3.

#### 8.5.3. Intercurrent Events

Handling of intercurrent events for the primary endpoint and secondary efficacy endpoints relevant to hospitalization/death and symptom duration are shown in Table 11.

Table 11.	Handling of Intercurrent Events
-----------	---------------------------------

Endpoint	Intercurrent event	Strategy	Description
Proportion of COVID-19–related hospitalization or all-cause death by Day 29	Discontinue randomized treatment prior to endpoint (due to AE, lack of efficacy, investigator's discretion,	Treatment policy	Ignore the occurrence of intercurrent events (use observed outcome)
Proportion of participants with all-cause hospitalization by Day 29	noncompliance with study drug, protocol violation, participant decision, lost to follow-up)	poney	
Proportion of participants with COVID-19–related MAVs or all-cause death by Day 29			
Proportion of participants with COVID-19–related MAVs by Day 29	Use of rescue medication	Treatment policy	Ignore the occurrence of intercurrent events (use observed outcome)
Proportion of participants with all-cause death by Day 29			
	Hospitalization for the treatment of COVID-19 or all-cause death	Composite policy	Hospitalization for the treatment of COVID-19 or all-cause death means never achieve symptom alleviation (censored at Day 14)
Time to COVID-19 symptom alleviation by Day 15	Discontinue randomized treatment prior to symptom alleviation (due to AE, lack of efficacy, investigator's discretion, noncompliance with study drug, protocol violation, participant decision, lost to follow-up)	Treatment policy	Ignore the occurrence of intercurrent events (use observed outcome)
	Use of rescue medication	Composite policy	Use of rescue medication means never achieve symptom alleviation (censor at Day 14)

AE = adverse event; COVID-19 = coronavirus disease 2019; MAV = medically attended visit

